7.8.2 Laboratory data

7.8.2.1 Laboratory data

The analyses of laboratory data will be descriptive in nature and will be based on BI standards [\(8\)](#). The same on-treatment periods as considered for the analysis of adverse events will be applied for laboratory values except for that the baseline laboratory value will be included in the 'on-treatment' period. Patients having at least one post-baseline laboratory value will be displayed in the descriptive analyses.

Descriptive statistics, including change from baseline and frequency of patients with transitions relative to the reference range, will be provided. CTCAE grades for applicable laboratory parameters will be calculated according to CTCAE version 4.03 [\(11\)](#). The following outputs will be presented:

- Transitions of CTCAE grade from baseline to worst laboratory value, from worst to last laboratory value during the on-treatment phase, and from baseline to last laboratory value.

Patients with missing CTCAE grade at baseline or no baseline value but post baseline values will be displayed in the category "Missing CTCAE grade at baseline". Laboratory values without CTCAE grading will be compared to their reference ranges and frequency tables will be provided for the number of patients within and outside the reference range at baseline and the last measurement on treatment.

Analysis of potentially clinically significant abnormal laboratory values, and handling of CTCAE grade -1 and -9 laboratory parameters, are described in the SOP for "Display and analysis of laboratory data" [\(8\)](#).

Proprietary confidential information © 2018 Boehringer Ingelheim International GmbH or one or more of its affiliated companies

7.8.2.2 Laboratory values of special interest

Drug-induced liver injury (DILI)

Criteria for 'potential' DILI can be found in Section 5.2.2.1 of the CTP.

Patients fulfilling these criteria will be followed up according to the procedures described in Section 10.3 of the CTP.

Patients with missing laboratory values for liver enzymes will be excluded from these analyses but will be presented separately in a listing.

Tabulations of hepatic enzyme elevations and liver laboratory values (see Section 5.2.2.1 of the CTP), including flags of true DILI cases, are created in accordance with the Food and Drug Administration (FDA) DILI guidance ([12](#)).

7.8.3 Vital signs

Only descriptive statistics are planned for this section of the report.

7.8.4 ECG

Any findings for ECG will be reported as AE. Separate ECG analyses will not be performed in this trial.

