- Grade 3: Severe or medically significant but not immediately life-threatening; hospitalisation or prolongation of hospitalisation indicated; disabling; limiting self care ADL
- Grade 4: Life-threatening consequences; urgent intervention indicated
- Grade 5: Death related to adverse event

Causal relationship of adverse event

Medical judgment should be used to determine the relationship, considering all relevant factors, including pattern of reaction, temporal relationship, de-challenge or re-challenge, and confounding factors such as concomitant medication, concomitant diseases, and relevant history. Assessment of causal relationship should be recorded in the eCRFs. The reason for the decision on causal relationship needs to be provided in the eCRFs.

Yes: There is a reasonable causal relationship between the investigational product administered and the adverse event.

No: There is no reasonable causal relationship between the investigational product administered and the adverse event.

Worsening of underlying disease or other pre-existing conditions

Worsening of the underlying disease or of other pre-existing conditions will be recorded as an adverse event or a SAE in the eCRF.

Changes in vital signs, electrocardiogram, physical examination, and laboratory test results

Changes in vital signs, ECG, physical examination and laboratory test results will be recorded as an adverse event or SAE in the eCRF if they are judged clinically relevant by the investigator.

Adverse events of special interests

DLTs and DLT-equivalent adverse events (see [Section 4.1.3.2](#) for definition), and DILI are defined as “adverse events of special interests”. Adverse events of special interests are to be reported in an expedited manner similar to SAE even if they do not meet any of the seriousness criteria (see [Section 5.2.2.2](#) for details).

If a DLT or a DLT-equivalent adverse event is observed, or the investigator determines any DILI is related to the study treatment, the administration of the investigational drug and/or application of concomitant therapy must be managed according to [Sections 4.1.3.5, 4.1.3.6](#), and [4.2](#).

The DILI is defined as followings:

- For patients with normal liver function (ALT, AST, and bilirubin within normal limits) at baseline:
An elevation of AST and/or ALT $\geq 3 \times$ ULN combined with an elevation of bilirubin $\geq 2 \times$ ULN measured in the same blood draw sample

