7.3.2 Secondary analyses

7.3.3 Safety analyses

The following measures will indicate how well BI 836845 is tolerated:

- Adverse events of special interest

- Adverse events leading to dose reduction
- Adverse events leading to discontinuation of study treatment
- The overall incidence and intensity of AEs according to Common Terminology Criteria, CTCAE version 4.03 ([R10-4848](#)) as well as relatedness of Adverse events to treatment
- SAEs
- Causes of death
- Vital signs
- Change from baseline for all laboratory tests
- ECOG performance status
- ECG

Frequency distributions, descriptive statistics and listings will be used to examine these variables.

Adverse event data from the first cycle will be presented separately. All data collected during the study will be assigned to a study period (e.g. screening, on-treatment, follow-up etc.) and be presented by BI 836845 dose level. Details will be provided in the TSAP.

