7.8.1 Adverse events

The analyses of AEs will be descriptive in nature. All analyses will be based on the number of patients with AEs (not the number of AEs).

For analysis multiple AE occurrence data on the CRF will be collapsed into an AE event provided that all of the following applies:

- All AE attributes are identical (Lowest Level Term (LLT), Common Terminology Criteria for Adverse Events (CTCAE) grade, action taken with trial medication, therapy

Proprietary confidential information © 2018 Boehringer Ingelheim International GmbH or one or more of its affiliated companies

required, seriousness, reason for seriousness, relationship, outcome, AE of special interest)

- The occurrences were time-overlapping or time-adjacent (time-adjacency of 2 occurrences is given if the second occurrence started on the same day or on the day after the end of the first occurrence)

For further details on summarisation of AE data, please refer to [\(2\)](#) and [\(6\)](#).

Adverse events will be coded with the most recent version of MedDRA. The severity of AEs will be scaled according to CTCAE (CTCAE version 4.03 [\(11\)](#)).

The analyses of adverse events will be based on the concept of treatment-emergent adverse events. That means that all adverse events with an onset between first treatment administration until end of the REP will be assigned as ‘on treatment’. All adverse events occurring before first drug intake will be assigned to ‘screening’ and all adverse events occurring after the residual effect period will be assigned to ‘post-treatment’; these AEs will be displayed in listings only. Adverse events will be displayed by the initial dose of Xentuzumab administered on the first day of treatment with Xentuzumab. Adverse events will be displayed by the initial dose of study medication administered on the first day of treatment

An overall summary of adverse events will be presented. The frequency of patients with adverse events will be summarised by treatment, primary system organ class and preferred term. Separate tables will be provided for patients with drug-related adverse events, adverse events leading to dose reduction, adverse events leading to discontinuation, serious adverse events, adverse events leading to death, other significant adverse events, adverse events of special interest, and adverse events fulfilling the DLT definition

Sorting order:

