7.8.5 Others

7.8.5.1 ECOG Performance Status changes

A shift table of the worst (highest) and last ECOG performance status category recorded on treatment or during follow-up by baseline category will be produced

Proprietary confidential information © 2018 Boehringer Ingelheim International GmbH or one or more of its affiliated companies

Proprietary confidential information © 2018 Boehringer Ingelheim International GmbH or one or more of its affiliated companies

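### The protocol lists ECG as a tolerability measure of its own, but SAP 7.8.4 plans no ECG analysis and the visible SAP does not declare the change

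*SAP*

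**What the plan says.** Protocol 7.3.3 lists the measures that will show how well the drug is tolerated. ECG is the last entry, apart from the AE entries. Of the whole list the protocol says "Frequency distributions, descriptive statistics and listings will be used to examine these variables", and that the data will "be presented by BI 836845 dose level. Details will be provided in the TSAP". Protocol 5.2.1 also names the 12-lead ECG as a safety assessment distinct from adverse events.

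The SAP handles the four measures that are not AE measures as follows:

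- Laboratory tests (SAP 7.8.2.1): "Descriptive statistics, including change from baseline and frequency of patients with transitions relative to the reference range, will be provided".
- Vital signs (SAP 7.8.3): "Only descriptive statistics are planned for this section of the report".
- ECOG performance status (SAP 7.8.5.1): "A shift table of the worst (highest) and last ECOG performance status category", by baseline category.
- ECG (SAP 7.8.4): "Any findings for ECG will be reported as AE. Separate ECG analyses will not be performed in this trial".

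On when an ECG change counts as an adverse event, protocol 5.2.2.1 says that such changes "will be recorded as an adverse event or SAE in the eCRF if they are judged clinically relevant by the investigator".

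**The concern.** The SAP removes the analysis of a measure that the protocol names, and offers a substitute that is narrower than it sounds. Under the protocol's recording rule, an ECG change reaches the AE tables only after the investigator has judged it clinically relevant. A reading below that bar is summarised nowhere in the visible plan.

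Protocol 5.4 gives monitoring of drug-induced change, ECG included, as the reason for the scheduled assessments. Protocol 3.1.1 has the ECGs recorded digitally and evaluated centrally. This is also the first administration of the drug to Japanese patients (protocol 2.1). As planned, a shift across a dose cohort made up of individually unremarkable readings would not be shown to a reader of the trial report.

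A reader who relies on SAP section 4 to learn where the analysis departs from the protocol would not find this departure there.

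**Working it through.** The plan gives no figure to reproduce. The check compares the texts and makes two simple counts.

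**1. Measures in protocol 7.3.3.**

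- AE, SAE or death measures: AEs of special interest; AEs leading to dose reduction; AEs leading to discontinuation; overall AE incidence, intensity and relatedness; SAEs; causes of death. That is 6.
- Other measures: vital signs, laboratory tests, ECOG performance status, ECG. That is 4.
- Total: 6 + 4 = 10.

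Of the 4 other measures, 3 have an output in the visible SAP 7.8 (7.8.2.1, 7.8.3, 7.8.5.1). ECG is the only one without.

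**2. Is the change declared?**

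- SAP 4.1 adds PK analyses only.
- SAP 4.2 drops named PK parameters with a reason, redefines duration of disease control and covers report timing.
- SAP 4.3 settles three points of terminology.
- The visible entries of the SAP history table do not mention ECG.

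So the sponsor used SAP 4.2 to declare and justify one dropped analysis, but not this one.

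**3. Does a later protocol change explain it?** The revised SAP is dated 10 December 2018. The protocol amendments are dated 4 July 2019 and 29 April 2022. Neither lists 7.3.3 among the changed sections; within section 7, amendment 1 lists only 7.3.4. The version gap therefore does not appear to explain the mismatch.

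**4. Is AE reporting equivalent?** SAP 7.8.4 covers any finding. Protocol 5.2.2.1 covers only changes judged clinically relevant.

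- If the protocol rule is followed, the SAP sentence is untrue, and results below the threshold are left out of the visible outputs.
- If the SAP sentence is followed literally, AE counts include findings that the protocol does not make AEs.

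**5. Scheduled ECGs through Cycle 1** (flow chart with note 9; protocol 5.2.5).

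- Per patient: 1 at screening + 3 on Day 1 + 1 on Day 15 = 5.
- Cohort of 3: 5 × 3 = 15.
- Cohort of 6: 5 × 6 = 30.
- Maximum of 24 patients, no replacements: 5 × 24 = 120.

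ECGs on Day 1 of each later cycle and at the end-of-treatment visit come on top. These counts show how much is scheduled, not how many abnormal readings would be missed.

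**The case against.** The strongest reply is that the protocol commits to little. It lists ECG in one word, ties no method to any single measure and leaves details to the SAP. SAP 7.8.4 then supplies the detail openly, under its own heading: ECG findings go to the AE outputs, which are frequency tables and listings. Those are shown by dose: "Adverse events will be displayed by the initial dose of Xentuzumab administered on the first day of treatment with Xentuzumab". On this view the sentence about findings merely assumes the protocol's recording rule. No ECG interval or category is named in the visible text, so there is no obvious variable to summarise. The stakes are also low: protocol 1.3.2 reports no adverse cardiovascular effects in monkeys, weekly doses up to 1800 mg were tolerated in an earlier trial (protocol 1.4) against a maximum of 1400 mg here, and statistics on 3 to 6 patients add little.

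Part of this stands. The SAP may choose the format, clinically relevant changes are still reported by initial dose, and the expected cardiac risk is low. If the central evaluation yields only categories, summary statistics are unnecessary.

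The rest does not answer the point. Leaving details to the SAP does not extend to dropping a named measure, and the protocol lists ECG separately from AE incidence. Low expected risk could justify a declared omission, but the visible SAP neither declares nor justifies one. The generous reading of the AE sentence concedes that it needs correcting.

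The technical TSAP, the table shells and some SAP sections are not available, so an ECG listing planned there cannot be excluded. An ECG summary planned there would contradict 7.8.4, which rules out separate ECG analyses for this trial.

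**Conclusion.** The concern holds. One of the four measures in protocol 7.3.3 that are not AE measures has no output of its own in the visible SAP 7.8. The departure is not declared in the visible SAP 4.1 to 4.3, and the substitute offered does not match protocol 5.2.2.1.

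The consequence is confined to descriptive safety reporting. The MTD is unaffected unless an ECG change is itself a DLT. This should be corrected, but it does not threaten the trial's main conclusion.

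The conclusion rests on the visible SAP text. The ECG counts assume the scheduled recordings are all made and no patient is replaced; the figure of 120 also assumes every cohort is filled and the optional expansion cohort of 6 is opened.

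**What to change.** **Preferred.** Replace SAP 7.8.4 with a descriptive ECG summary and a frequency table of ECG findings by dose cohort, plus a listing. If the central evaluation returns only categorical readings, the frequency table and listing are enough.

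**If the omission is kept.** Declare and justify it in SAP 4.2 as a change from protocol 7.3.3. This makes the departure traceable but leaves the protocol's analysis undone, so it is the weaker option.

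**In either case.** Correct the sentence in 7.8.4 so that ECG changes are reported as AEs only when judged clinically relevant, as protocol 5.2.2.1 has it.

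**Cost.** The preferred fix needs a few descriptive tables and one listing, assuming the central ECG results reach the trial database. The documents do not state this. Protocol 3.1.1 exempts the rollover part from data transfer and central evaluation, which suggests that both apply before it. The weaker option costs one sentence in SAP 4.2 and one corrected sentence in 7.8.4.

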7.8.5 Others

7.8.5.1 ECOG Performance Status changes

A shift table of the worst (highest) and last ECOG performance status category recorded on treatment or during follow-up by baseline category will be produced

Proprietary confidential information © 2018 Boehringer Ingelheim International GmbH or one or more of its affiliated companies

Proprietary confidential information © 2018 Boehringer Ingelheim International GmbH or one or more of its affiliated companies

10 HISTORY TABLE

Table 10: 1 History table

Version	Date (DD-Mmm-YY)	Author	Sections changed	Brief description of change
Final	26-Jun-17	[REDACTED]	None	This is the final TSAP without any modification
Revised	10-Dec-18	[REDACTED]	Section 4.2 Section 6.2 and 7.1.2 Section 7.1.2 Section 7.9.1 and section 7.9.2 Section 7.9.3	
Added the description the CTR report timing.
 
[REDACTED]
 
Terminology changed from “Protocol violation” to “Protocol deviation” followed latest SOP.
 
Appendices section from 16.1.9.2.3 to 16.1.13.1.3 changed followed latest SOP.
 
Provided more details on the biomarker analyses.
 
Deleted the dose proportionality PK analysis based on the PK colleagues discussion.

